Complete remission: Complete remission is defined as recovery of platelets (confirmed by platelets  $\geq 150,000/\mu\text{L}$  and LDH  $\leq 2 \times \text{ULN}$  at 48 hrs after initial platelet response) and absence of exacerbation.

Initial platelet recovery: Date of initial platelet recovery is defined as the first occurrence of platelets  $\geq 150,000/\mu\text{L}$  which is **confirmed** 48 hours later by platelets  $\geq 150,000/\mu\text{L}$  and LDH  $\leq 2 \times \text{ULN}$ . For example, if platelets reach  $\geq 150,000/\mu\text{L}$  on Day 5, are not confirmed at Day 7, reach  $\geq 150,000/\mu\text{L}$  again on Day 10 and are confirmed at Day 12, the initial platelet recovery occurs on Day 10. Initial platelet recovery and confirmation dates will be determined using the actual lab results, following standardisation to consistent units.

Time to Response: Time to response will be calculated as the number of days, hours and minutes (represented by number of days with two significant digits after the decimal point) from study drug administration to initial platelet recovery, as defined above. An

---

observation is censored if the observation does not meet the defined time interval of 30 days, due to any cause of loss-to follow-up (including death), or endpoint not being reached.

Subjects that attain confirmed platelet response:

Time-to-Response = [Date and time (hrs, min) of initial platelet recovery] – [Date and time (hrs, min) of first study drug administration]

Exacerbation: Exacerbation of TTP is defined as recurrent thrombocytopenia following a confirmed platelet response and requiring a re-initiation of daily PE treatment  $\geq 1$  day but  $\leq 30$  days after the last daily PE.

Relapse: Defined as de novo event of TTP that occurs later than 30 days after the last daily PE.

First PE: Defined as start of PE.

First on-study PE: Defined as first PE received after randomisation.

In case first on-study PE is not first PE, then first on-study PE should be started within 24 hours (after the end) of the first PE. If not it is considered major protocol deviation.

Overall duration of study treatment exposure (days): Defined as date of last dose of study treatment – date of first dose of study treatment + 1

Duration of study treatment exposure during daily PE (days): Defined as date of last dose of study treatment during the daily PE period – date of first dose of study treatment during the daily PE period + 1

Duration of study treatment exposure post daily PE (days): Defined as date of last dose of study treatment – date of first dose of study treatment after the daily PE period + 1

RR interval for electrocardiogram (ECG): Defined as 60,000 / Heart Rate

---

#### 4. EFFICACY PARAMETERS

##### Clinical Outcomes:

- Time-to-response of treatment, defined by a recovery of platelets  $\geq 150,000/\mu\text{L}$ . This response must be confirmed at 48 hours after the initial reporting of platelet recovery above  $150,000/\mu\text{L}$  by a *de novo* measure of platelets  $\geq 150,000/\mu\text{L}$  and  $\text{LDH} \leq 2 \times \text{ULN}$
- Number and percentage of subjects with confirmed platelet response
- Number and percentage of subjects with complete remission
- Number and percentage of (subjects with) exacerbations of TTP and time to first exacerbation of TTP
- Daily PE data (total volume of plasma units administered and number of days of PE), including serious adverse events (SAEs) related to PE treatment
- Total mortality within the daily PE treatment period and within the subsequent study drug treatment period (including tapering). Note that tapering of PE is considered to be part of the subsequent study drug period rather than as part of the daily PE period.
- Number and percentage of subjects relapsing of TTP for a maximum of 1 year and time to first relapse of TTP
- Number and percentage of subjects with platelets  $\geq 150,000/\mu\text{L}$  at day 30 of study drug administration (last treatment day visit) and at 1 month follow-up time point
- Neurocognitive function (adults only), as measured by a neurocognitive test battery, at complete remission and at 1 year follow-up. Remission is defined as the absence of need for PE treatment  $\geq 30$  days. In adults, this test will be preceded by the Glasgow Coma Score to measure the state of consciousness of the subject. For adolescents, neurocognitive function is not measured by a neurocognitive test battery; only the Glasgow Coma Score will be assessed.
- The Glasgow Coma Score which indicates the degree of consciousness, is sum of the Eye Opening, Verbal and Motor Response scores.
- Improvement of organ dysfunction and improvement of TTP related signs and symptoms
- Determination of biomarkers of TTP including but not limited to disintegrin-like and metalloprotease with thrombospondin repeats 13 (ADAMTS13) activity levels, including baseline functional inhibitors (see also PD assessments)

**Clinical Outcome of Special Interest parameters:**

- Plasma exchange (PE)
- Transfusion of red blood cells (RBC)
- Peripheral and/or central blood line placement and replacement for PE
- Concomitant medication other than PE, i.e. for treatment of TTP, e.g. corticosteroids, rituximab
- Modified Immune Thrombocytopenic Purpura (ITP) bleeding score
- Neurocognitive battery which is comprised of the Computerised neuropsychological test battery (CNTB), the Category Fluency Test and the Letter Fluency Test

**Laboratory Markers of Disease:**

- Platelets
- ADAMTS13 activity, including baseline functional inhibitors (central laboratory)
- Cardiac marker (Troponin T [TnT] or Troponin I [TnI])
- Brain natriuretic peptide or B-type natriuretic peptide (BNP); N-terminal pro B-type natriuretic peptide or N-terminal pro brain natriuretic peptide (NT-proBNP)
- Brain damage markers (Neuron specific enolase [NSE], Protein S-100 beta [Sβ100]) (central laboratory)
- PD: Ristocetin cofactor activity (RICO) (central lab), von Willebrand factor antigen (vWF Ag) and propeptide (central lab), coagulation factor VIII (FVIII) chromogene (central lab)

**5. SAFETY PARAMETERS****Laboratory parameters:**

- Haematology
  - Full blood count, including red blood cells (RBC), haemoglobin, haematocrit, mean corpuscular volume (MCV), mean corpuscular haemoglobin (MCH), mean corpuscular haemoglobin concentration (MCHC), white blood cells (WBC) and differential blood count
  - Reticulocytes

- 
- Optical platelet count (if not available, can be replaced by measurement based upon impedance)
  - Immature platelet fraction (can be omitted)
  - Blood chemistry
    - Glucose
    - Haptoglobin
    - Gamma-glutamyl transferase (GGT) (screening only)
    - Bilirubin (total) (screening and baseline only)
    - Alkaline phosphatase (AP) (screening and baseline only)
    - Aspartate transaminase (AST)
    - Alanine transaminase (ALT)
    - Lactate dehydrogenase (LDH)
    - C-reactive protein (CRP)
    - Human chorionic gonadotropin (hCG) (for women, only if urine pregnancy test is not feasible or inconclusive) (baseline only)
    - Rheumatoid factor (baseline only)
    - Antinucleic acid (baseline only)
    - Iron, ferritin, transferrin (baseline only)
    - Creatinine, blood urea nitrogen (BUN), uric acid
    - Protein, albumin
    - Sodium (Na), Potassium (K), Calcium (Ca), Magnesium (Mg), Chloride (Cl)
  - Urinalysis
    - pH
    - Specific gravity
    - Protein
    - Glucose
    - Ketones
    - Bilirubin
    - Blood
    - Nitrite
    - Urobilinogen
    - Leukocytes

- 
- Urine pregnancy test for female subjects (hCG only)
  - Virus serology
    - Human immunodeficiency virus type 1 and type 2 (HIV1 and HIV2) antibodies at screening
    - Surface antigen of hepatitis B virus (HBV HbsAg) and hepatitis C virus (HCV) antibodies at screening
  - Coagulation variables (local lab)
    - Activated partial thromboplastin time (aPTT)
    - Prothrombin time (PT)
    - International normalized ratio (INR)
    - Fibrinogen
    - vWF Ag
    - FVIII chromogenic or alternative method (e.g. one stage clot test) if not available in the local lab
    - Lupus anticoagulant
    - Anticardiolipin antibodies (antiphospholipid):
      - Immunoglobulin G (IgG), Immunoglobulin M (IgM) and Immunoglobulin A (IgA)
  - Blood typing (ABO and Rhesus factor [Rh]) and direct antiglobulin test (DAT)

### **Physical Examination**

- Dermatologic
- Immunological / Allergies (other than to medication)
- Head, Eyes, Ears, Nose and Throat (HEENT)
- Endocrine
- Respiratory
- Cardiovascular
- Genitourinary / Reproductive
- Musculoskeletal
- Neurological
- Psychological / Psychiatric
- Other Symptoms

**Vital Signs**

- Systolic and Diastolic Blood Pressure
- Heart Rate
- Body Temperature
- Height (screening only)
- Weight

**Bleeding Events:**

- Clinically relevant bleeding
- Modified ITP bleeding score

**Cardiovascular Monitoring:**

- 12-lead electrocardiogram (ECG) parameters:
  - Heart rate
  - PR
  - QRS
  - QT
  - QTc (Bazett)
  - RR

**Glasgow Coma Score**, which indicates the degree of consciousness, is sum of the Eye Opening, Verbal and Motor Response scores

**Adverse Events**, which are defined as any untoward medical occurrence which does not necessarily have a causal relationship with study treatment

**Immunogenicity**

Anti-drug antibodies (ADA) in serum as determined by an appropriate assay technique

**6. STATISTICAL METHODOLOGY**

---

## 6.1 Statistical and Analytical Issues

### 6.1.1 Statistical Methods

All data will be summarised by treatment group. In addition, where appropriate, a total overall group column will be included to summarise all subjects. Where appropriate, data will be summarised by treatment group and visit or whenever the assessment is done (e.g. the 1 and 3 week post-last day PE sampling may be done at the weekly visit, even if not at exactly 1 or 3 weeks).

All data will be listed and some selected variables will be tabulated or presented graphically, and will be noted where appropriate.

In summary and analysis tables of continuous variables, the minimum and maximum statistics will be presented to the same number of decimal places as the original data. The mean, median, quartiles, Least Squares mean (LS mean), and 95% Confidence Interval (CI) will be presented to one more decimal place than the original data, the standard deviation (SD) and standard error (SE) will be presented to two more decimal places than the original data. Standard descriptive statistics (number of subjects with data available [n], mean, SD, median, minimum and maximum) will be presented in summary tables. The LS mean, SE and 95% CI will be presented in the statistical analysis outputs as appropriate.

In summary tables of categorical variables, the number of non-missing observations and percentages will be presented. The denominator for each percentage will be the number of subjects within the population of interest [N] (unless otherwise specified).

All hypothesis testing will be 2-sided unless otherwise specified and carried out at the 5% significance level and designed to evaluate the superiority of ALX-0081 to placebo.

P-values will be rounded to three decimal places. P-values less than 0.001 will be reported as <0.001. P-values greater than 0.999 will be reported as >0.999.

Should any of the statistical methods (other than the primary endpoint analysis) proposed prove unsuitable during the final analysis, more appropriate methods will be used, and any changes documented in the CSR, including the rationale for use.

All statistical analysis will be performed using SAS® v9.2 or higher.

### 6.1.2 Handling of Dropouts and Missing Data

The primary, secondary and longer term endpoint analyses will be based on available data. No imputations will be made for missing data unless otherwise specified.

If a subject had a PE prior to being randomised then there will be no replacement of missing baseline values by screening values. If a subject did not have a PE prior to being randomised then missing baseline values will be replaced by screening values. Missing data post-baseline will not be estimated or imputed for any of the parameters.

### 6.1.3 Pooling of Investigator Sites

Data will be pooled from multiple sites for this analysis. The justification for pooling is made on a clinical basis (Meinert, 1986). The basis for pooling comes from three critical factors. The study sites must implement one common protocol. The sponsor must provide very close monitoring of study site compliance, and the study sites must use common data collection procedures.

### 6.1.4 Determination of Sample Size

The primary endpoint of time-to-response of blood markers (defined as time-to-response) is monitored in a survival setting. The time-to-response of blood markers comprises recovery of platelets  $\geq 150,000/\mu\text{L}$ . Accrual period was taken as 1.5 years. Actual accrual time is longer than 1.5 years; however there is no impact on the sample size. Zero to time to event period is set at 30 days. As median time-to-response for the control group we take 6 days (this information is calculated based upon Bandarenko *et al.*). For the treated group with ALX-0081 we assume a 44% risk reduction corresponding to a reduction in median time to event of 2.64 days, and ultimately resulting in a time-to-response of 3.36 days. The hazard ratio is defined in the SAS code as the ratio of control versus experimental (ALX-0081) treatment thus equaling to  $6/3.36=1.786$ . The sample size calculations are performed based on a log-rank test, aiming for a power of 80%, tested 1-sided at 2.5% significance level with 1:1 randomisation. Note that we assume that 15% of subjects would be lost-to-follow-up. The latter is justifiable because the active follow-up period (time of first study drug administration to time to event) only

---

equals 30 days. Based on the above described assumptions a sample size of 110 adult subjects is required. As subjects can be replaced, the ITT population may be larger than 110 subjects.

### 6.1.5 Changes to Planned Analyses from the Protocol

- Section 4.1.2 of the protocol describes the following secondary endpoint:  
Resolution or improvement (improvement of  $\geq 1$  grade in the CTCAE v4.0 scale) of TTP-related signs and symptoms as captured on the physical examination and as adverse events.  
  
At the time of writing this Statistical Analysis Plan, it is apparent from the design of the CRF that the CTCAE grade is recorded only once per event. Therefore it is not possible to determine if or when the CTCAE grade of a particular event has improved by  $\geq 1$  grade. As a consequence, for the adverse events part of this endpoint only resolution of events (defined as having a stop date and an outcome of either 'resolved' or 'resolved with sequelae') will be considered.
- Section 4.1.2 of the protocol describes the following secondary endpoint:  
Resolution of non-focal neurological symptoms as defined by neurocognitive function at complete remission, measured by a neurocognitive test battery.  
  
The intention was to define neurocognitive function as having a CNTB average summary score immediately post hospital discharge that is equal to or higher than at Baseline. At the time of writing this Statistical Analysis Plan, it is apparent from the data for the CNTB that the majority of subjects do not have their first CNTB assessment until after they have received study treatment. The time from first treatment to first CNTB assessment is not consistent across subjects, such that a homogeneous Baseline time point cannot be defined. It is therefore not appropriate to derive this endpoint based on change from Baseline because the resulting data will have no meaningful interpretation. It has been agreed that the CNTB will be summarised by descriptive statistics at each time point for actual results only; change from Baseline will not be calculated.

- Section 4.1.3 of the protocol describes the following secondary endpoint:  
Resolution of non-focal neurological symptoms as defined by neurocognitive function at one year follow-up, measured by a neurocognitive test battery.  
The intention was to define neurocognitive function as having a CNTB average summary score 12 months post hospital discharge that is equal to or higher than at Baseline. As explained in the previous bullet, a homogeneous Baseline time point cannot be defined and it is therefore not appropriate to derive this endpoint based on change from Baseline; it has been agreed that the CNTB will be summarised by descriptive statistics at each time point for actual results only; change from Baseline will not be calculated.

## **6.2 Subject Characteristics**

### **6.2.1 Subject Disposition**

Complete accounting of subject participation (from entrance into the study through to final visit) in the study is presented in the summary table for subject disposition.

Subject disposition will be summarised by treatment group and overall for all subjects. The number of subjects screened and the number of subjects who failed screening will be presented. In addition, the number of subjects randomised and the number and percentage of randomised subjects who complete the study, discontinue the study, and reasons for discontinuation from the study will be summarised. The number and percentage of randomised subjects within each population by treatment and overall will also be summarised.

Subjects who discontinued the study early and were replaced will be included in the disposition listing.

### **6.2.2 Protocol Deviations**

A protocol deviation is defined as failure to fully comply with the study protocol. The deviation can be classified further as:

- 
- Minor Protocol Deviation – does not have an impact on the subject’s rights, safety or wellbeing, or the completeness, accuracy and reliability of the study data
  - Major Protocol Deviation – may affect the subject’s rights, safety or well being and/or the completeness accuracy and reliability of the study data

The sponsor will make any decisions regarding whether any subjects or any individual parameters pertaining to a subject will be excluded from the safety and efficacy evaluations when the protocol deviation is considered to have a negative impact on scientific aspects and interpretation of the study results.

Major protocol deviations will be excluded from the PP population.

All major protocol deviations will be listed. Major protocol deviations will be summarised by treatment group and overall for the ITT population.

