10.1 Study Populations

Populations for the primary and secondary endpoint analyses

The primary analysis population will be the intent-to-treat (ITT) population, which will consist of all randomised subjects according to the randomised treatment assignment. In addition, for the efficacy analyses, the per protocol population (PP) will be used. The PP population will be a subset of the ITT population and will consist of all randomised subjects, according to the randomised treatment assignment, with exclusion of all major protocol violators.

Population for the safety analysis

The safety population will consist of all subjects who received at least one dose of study drug, with treatment assignment designated according to actual treatment received.

Population for the PK analyses

The PK analyses will be performed on the PK population, which will consist of all subjects who have received study drug and for whom the primary PK data are considered to be sufficient and interpretable.

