## 2. STUDY POPULATIONS

Four subject populations will provide the basis for all statistical analyses, data evaluations and summaries of the adult subjects.

Safety Population: The safety population includes all subjects who received at least one dose or partial dose of study drug, with treatment assignment designated according to actual treatment received.

Actual treatment received is not collected in the study database. [REDACTED] [REDACTED] will record the details of any subject receiving treatment that does not correspond to their randomised treatment assignment. Actual treatment received will be defined as being equal to randomised treatment assignment for a particular subject unless the incorrect treatment was administered for the majority of the subject's time on treatment.

Intent-to-Treat (ITT) Population: The intent-to-treat population includes all randomised subjects, according to the randomised treatment assignment. The ITT population will be the primary population of interest for efficacy analyses.

Per-Protocol (PP) Population: The per-protocol population includes all randomised subjects, according to the randomised treatment assignments who have no major protocol deviations (see [Appendix II](#)) and satisfactorily complete the study. The PP population will be a subset of the ITT population and will be the secondary population of interest for efficacy analyses.

Subjects to be excluded from the PP Population will be defined prior to the database lock according to criteria as per [Appendix II](#) without regard to study drug assignment. [Appendix II](#) describes the major protocol deviations affecting the statistical analysis of the study and their derivation; an extensive tracker of all clinical protocol deviations is maintained separately by [REDACTED].

---

Pharmacokinetic (PK) Population: The PK population will consist of all subjects who received the study drug and for whom the primary PK data are considered to be sufficient and interpretable. The PK analysis will utilize the PK population.

Adolescent subject data will be described separately from the adult subjects. There will be no formal statistical analysis of adolescent data, only listings. Data for adolescent subjects will be grouped separately from adult subject data within the listings.

---

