### *Censoring and event plan*

The primary endpoint in this trial is time to (initial) response. The event or response is defined as confirmed recovery of platelets above or equal to  $150,000/\mu\text{L}$ .

- Confirmed response means that 48 hours after the initial response, platelets remain above or equal to this cut-off (*de novo* measurement), and lactate dehydrogenase (LDH)  $\leq 2 \times$  upper limit of normal (ULN).
- ‘Time to’ is defined as time in days, hours and minutes between the event and the first administration of study drug. The initial time of reaching platelets above or equal to 150,000/ $\mu$ L is considered as the time of recovery of platelets, and must occur within 30 days after first administration of study drug. However, this initial recovery of platelets must be confirmed at 48 hours after initial reporting, implying that time of confirmation may be 48 hours later than 30 days after first administration.

Assessment of the primary endpoint is performed by using a one-sided log-rank test at 2.5% significance level. A Kaplan-Meier (KM) analysis with time-to-response as the endpoint and treatment group as the independent variable, and stratified for absence/presence of one PE session prior to randomisation, will be performed on the ITT population (all randomised subjects).

An observation is censored if the observation does not meet the defined time interval of 30 days after first administration of study drug medication, due to any cause of loss to follow-up (including death), or endpoint not being reached within the defined time interval. Only right censoring is applicable to this trial. In **Table 1**, different potential response (censoring/event) scenarios are presented.

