**Table 1: Censoring/event scenarios (for ITT and PP analysis of confirmed platelet response)**

Case	Description	Time at risk/ Time to recovery of platelets (days)	Responder	Censored (No = 0; Yes = 1)
1	No event in 30 days of continuous daily PE a	30	No	1
2	At day 30, confirmed recovery of platelets (per protocol)	30	Yes	0

Case	Description	Time at risk/ Time to recovery of platelets (days)	Responder	Censored (No = 0; Yes = 1)
3	At day x b (1 st measurement of platelet recovery), confirmed recovery of platelets, ideal case (per protocol)	x	Yes	0
4	No event occurred and subject is no longer in trial at day x b (including replaced subjects who are dosed)	x	No	1
5	At day x b (1 st measurement of platelet recovery), subject has recovery of platelets, however, missing data at 48 hours later, and no subsequent confirmation on platelet count during daily PE (no more daily platelet measurements) c	x	No	1
6	No recovery of platelets, however, daily PE stopped (daily PE considered surrogate for response d ). Except if PE stopped due to AE e (then idem case 4)	Time of last daily PE	No	1
7	Subject not dosed (after randomisation)	1	No	1

a PE = plasma exchange.

b At day x within 30 days assessment period.

c No subsequent confirmation during daily PE, since daily PE has been stopped by Investigator for clinical response which does not meet protocol definition of response.

d Certain subject's platelet counts 'hover' around 150,000/ $\mu$ L, and in clinical practice, PE is stopped.

e Start and stop dates of adverse events related to PE will need to be compared to PE stop dates in order to identify PE stopped due to AE.

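### SAP 6.2.2 lets the sponsor exclude subjects or single parameters from safety and efficacy evaluations for a deviation, which is not reconciled with ITT and Safety populations that have no such exception

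*SAP*

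**What the plan says.** Under SAP 6.2.2 the sponsor decides whether "any subjects or any individual parameters pertaining to a subject will be excluded from the safety and efficacy evaluations". The only condition is that this happens "when the protocol deviation is considered to have a negative impact on scientific aspects and interpretation of the study results". A separate sentence then deals with the per-protocol set: "Major protocol deviations will be excluded from the PP population".

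The population definitions make no allowance for deviations. SAP section 2 states: "The intent-to-treat population includes all randomised subjects, according to the randomised treatment assignment". Protocol 10.1 makes ITT the primary analysis population, "which will consist of all randomised subjects according to the randomised treatment assignment". In both documents the safety population is everyone who received study drug, and the SAP counts even a partial dose. SAP 6.3.1 (Censoring and event plan) runs the primary analysis on ITT and glosses it as all randomised subjects. SAP 6.4 puts all safety data on the safety population.

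SAP section 2 also says how per-protocol exclusions are made: by the Appendix II criteria, before database lock, and without reference to treatment.

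**The concern.** A discretionary exclusion rule that reaches the ITT and safety analyses defeats the purpose of defining those populations in advance. The primary comparison is protected because everyone randomised is counted. The safety comparison is protected because everyone dosed is counted. As written, 6.2.2 gives a route round both, on a subjective test, with no time limit and nothing to keep the decision independent of arm or outcome.

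The link to safety is concrete. Appendix II classes as major deviations both the failure to stop study drug when clinically relevant bleeding occurs and restarting it before the stated vWF:Ag and FVIII conditions are met. SAP 6.4.6 calls clinically relevant bleeding the main potential risk of the drug. A subject with the key safety event may therefore also carry a deviation that could trigger the clause.

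**Working it through.** **1. Can the clause be read as applying to the per-protocol set only?** The wording does not fit that reading.
- It names safety evaluations. SAP section 2 describes the per-protocol set as a population for efficacy analyses, and 6.4 puts all safety data on the safety population. A clause limited to per-protocol would have no safety analysis to act on.
- It reaches individual parameters. Per-protocol membership is decided for the whole subject.
- Per-protocol exclusion has its own sentence immediately afterwards.

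**2. Do the section 2 safeguards cover it?** No. The criteria, the timing and the treatment-neutral condition are all attached to per-protocol exclusions. 6.2.2 classifies a deviation as major in general terms (a possible effect on rights, safety or data quality), so its trigger is not tied to the Appendix II list. The SAP does ring-fence the primary analysis elsewhere: 6.1.1 allows substitute statistical methods except for the primary endpoint. 6.2.2 has no similar carve-out. SAP 6.1.5, which lists changes from the protocol, does not mention an exception to ITT or Safety.

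**3. How does the rest of the SAP treat deviators?** It keeps them.
- 6.2.2 itself summarises major deviations for the ITT population, so deviators are ITT members.
- Appendix II lists randomised-but-untreated as a major deviation. Table 1, case 7 keeps such subjects in the primary analysis, censored at day 1.
- Appendix II lists wrong treatment as a major deviation. Section 2 has a rule for the arm in which such subjects are counted for safety.

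The discretionary sentence therefore contradicts the rest of the plan, and no text says which statement governs.

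**4. Scale.** The contradiction does not depend on any figure. For context, the planned size can be reproduced. Inputs from protocol 10.4 and SAP 6.1.4: medians 6 and 3.36 days, ratio 6/3.36 = 1.786, one-sided 2.5%, power 80%, 1:1 allocation, 15% loss, 30-day window.
- Events (Schoenfeld) = 4 × (1.960 + 0.842)² / (ln 1.786)² = 31.4 / 0.336 = 93.4, so 94. Then 94 / 0.85 = 110.6, so 111, against the stated 110.
- With 110 subjects, 110 × 0.85 = 93.5 events gives 80.0% power.
- Under exponential times, the probability of response by day 30 is 1 − 2^(−30/6) = 0.969 on control and 1 − 2^(−30/3.36) = 0.998 on ALX-0081, mean 0.983. Expected events are then about 93.5 × 0.983 = 91.9.

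The next table is an illustration on **assumed** inputs that are not in the documents. Power uses (110 − k) × 0.85 events. Type I error comes from 20,000 null simulations: 55 per arm, exponential times with median 6 days, 15% of subjects given a random censoring time, an unstratified log-rank test, and a deviation in a random 30% of the ALX-0081 arm.

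| Removed (k) | Power, non-selective | Type I error, non-selective | Type I error, k slowest ALX-0081 deviators removed |
|---|---|---|---|
| 0 | 80.0% | 2.6% | 2.6% |
| 1 | not run | 2.6% | 4.3% |
| 2 | not run | 2.6% | 5.9% |
| 3 | 79.0% | 2.6% | 7.1% |
| 5 | 78.2% | 2.5% | 8.7% |

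The simulation error near 2.5% is √(0.025 × 0.975 / 20,000) = 0.11 percentage points, so the k = 0 row agrees with the nominal level. Removal unrelated to outcome does little harm. Any damage comes from selective removal, which the clause does not prevent.

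**The case against.** The strongest reply is that this is one loosely drafted sentence, placed under Subject Characteristics, that says who decides. The sections that govern the analyses are explicit, and step 3 shows that deviation-based exclusion otherwise operates through the per-protocol set. Much of this stands, and it rules out four stronger readings that a reader might infer.

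- **That 6.2.2 overrides ITT and Safety.** The SAP never gives it precedence over section 2. The supportable statement is that the two conflict and are not reconciled.
- **That adverse events could be made to disappear.** SAP 6.4.1 lists all recorded adverse events, 6.2.2 lists all major deviations, and 6.2.1 counts randomised subjects in each population by treatment. A summary table could omit a subject, but the event would remain in the listings.
- **That the people deciding know the arm.** Protocol 7.5 says the investigator is told the treatment. Neither document says whether the sponsor staff who judge deviations are blinded.
- **That type I error is inflated.** The inflated figures above rest on an assumed deviation rate and deliberate removal of slow responders. They are not a property of the plan.

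The reply does not dispose of the point. The sentence reaches safety evaluations and single parameters in plain words, and nothing in section 2 shields ITT or Safety from it.

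**Conclusion.** The point holds as an unreconciled contradiction. SAP 6.2.2 grants an open-ended, subjective power to exclude subjects or parameters from safety and efficacy evaluations. The population definitions and the analysis sections allow no such exception, and the pre-lock, treatment-neutral safeguards protect only the per-protocol set. If the power were used, the primary log-rank test or the safety summaries could lose subjects. The documents do not say whether or how it would be used, so the size of any bias cannot be stated, and no misuse is implied. The conclusion rests on the wording alone. It goes beyond a missing detail because the SAP states a discretionary rule that touches the primary and safety analyses. It should be corrected before database lock.

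**What to change.** Replace the discretionary sentence in SAP 6.2.2 with:

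> Protocol deviations affect membership of the PP population only (and PK evaluability as defined in section 2), decided and documented before database lock without knowledge of treatment assignment. No randomised subject is excluded from the ITT analyses, and no subject who received at least one full or partial dose is excluded from the Safety analyses, and none of their data are removed from those analyses, because of a protocol deviation. Any other deviation-based exclusion is presented only as a labelled sensitivity analysis.

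This wording respects the existing definitions. Randomised subjects who were never dosed stay out of Safety, and PK evaluability keeps its own test. It bars removal on the ground of a deviation; it does not address measurements shown to be invalid for another reason.

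The cost is one SAP sentence. Sample size and power do not change, no data collection is added, and protocol 10.1 needs no amendment because it already defines the populations without a deviation exception.
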